7.3.2 Warfarin Compliance

Warfarin compliance will be monitored by means of the international normalised ratio (INR) rather than by pill counts as it is a more accurate and biologic measure of pharmacodynamic effect. The quality of warfarin therapy for each patient will be assessed by reporting the number of INR values within the indicated therapeutic target range (2.0 - 3.0) as well as those above and below this range. The Rosendaal method [10] will be used to evaluate the percentage of time that a patient's INR is in range (i.e. time in therapeutic range [TTR]). For each calendar month, the mean of all INR values will be reported. This will be calculated for each patient, for each centre, for each country and for the whole study. The mean percentage of time of INR in range will be calculated for each centre and each country during the trial conduct to monitor the INR control. The percentage of time of INR in range for each country and for the trial will be reported at study end.

For patients who had a temporary discontinuation of study warfarin, INR values taken in the time interval between the day after the temporary discontinuation and restart of medication will not be counted. If INR is evaluated during the first week after randomisation, those INR values will not be used in calculating TTR.

The Rosendaal method: assume the INR value between two measurements will vary linearly from the value of the first to the value of the second measurement, divide the time between two measurements in days, fit a linear equation using the two measured INR values, and then calculate the INR for each day in the interval. The percentage of time when INR is in target range is calculated for each patient.

Furthermore, the number and frequency of patients with percentage of time in INR target range by cutpoints 45, 55 and 65%, as well as 60 and 75% will be presented for the trial.

Descriptive statistics will be provided for the number of INR measurements per months.

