### Patient randomised to receive warfarin

Patients randomised to warfarin will start the trial medication on the day of randomisation. If they are on oral anticoagulation (VKA) at the moment of randomisation, it needs to be confirmed that INR is  $<3.0$  before trial medication is started. If the INR is  $\geq 3.0$ , warfarin must not be started until the INR is in the therapeutic range. Actual date and time of administration of the first dose of warfarin are to be recorded in the CRF.

Initial parenteral anticoagulation should be continued together with study warfarin if INR is  $<2.0$ . Initial parenteral therapy should be discontinued as soon as INR is  $\geq 2.0$  (one measurement). Randomisation should occur no later than 15 days after start of UFH /

Proprietary confidential information © 2017 Boehringer Ingelheim International GmbH or one or more of its affiliated companies

LMWH. For patients randomised to receive warfarin, UFH / LMWH may continue beyond day 15 until the requirement of INR  $\geq 2.0$  has been met.

INR monitoring should continue and warfarin doses adjusted to maintain an INR between 2.0 and 3.0.

Warfarin tablets are to be taken with water, preferably at the same time each day.

Warfarin patients will usually be managed by their Investigator. However, Investigators will also be able to assign INR monitoring to a local anticoagulation clinic. All dose adjustments will be done according to usual clinical practice, taking into account that tablets may not be split (i.e. only whole tablets to be taken by the patient). The Investigator will be responsible for reporting INR results and the dose of warfarin prescribed.

For patients randomised to warfarin, the INR measurements should be performed as necessary for dose adjustment and maintenance until the EOT visit in order to obtain the target INR as soon as possible and to avoid over- or under-dosing. INR measurements should be performed daily from the start of treatment until concomitant heparin treatment is stopped (if applicable), at least once every two weeks for the first three months thereafter and monthly subsequently. More frequent INR measurements will be done as necessary at the discretion of each Investigator or anticoagulation clinic.

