To aid investigators, a validated nomogram will be provided which will indicate recommended dose changes and INR re-testing times for different INR values. This nomogram requires more frequent INR monitoring after out-of-range INR values have occurred.

Patients with protein C deficiency are at risk of developing skin necrosis when starting warfarin treatment. Therefore, for patients with known protein C deficiency, therapy should be introduced slowly without a loading dose of warfarin even if heparin is given. Patients with protein S deficiency may also be at risk and it is advisable to also introduce warfarin therapy slowly in such patients.

Numerous factors, alone or in combination, may influence the patient's response to anticoagulants. Thus to ensure adequate control it is recommended that additional INR measurements are performed when other medications are initiated, discontinued or taken irregularly and/or in case of diet changes. All patients should be educated about potential interactions with other medications, herbal preparations and foods and about the importance of monitoring. INR measurements can be performed independently from the scheduled study visits (see [Flow Chart](#)), however all available INR values should be entered into the CRF. It is critical to obtain the best possible level of INR control.

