### **6.2.2 Treatment period(s)**

All assessments for the visits in the treatment phase are detailed in the Flow Chart.

After eligibility has been confirmed and all Visit 1 procedures completed, Visit 2 can be conducted including randomisation via IRT. IRT should not be called in advance of Visit 2, as randomisation of a patient cannot be reversed.

At the start of Visit 2, it should be ensured that all Visit 1 procedures have been successfully completed. Visit 2 procedures are outlined in the Flow Chart. Restricted medications as outlined in Section [4.2.2](#) will be stopped if applicable.

Randomisation should occur as soon as the patient is stable and patient eligibility is confirmed, at 5 days (120 hours) and up to a maximum of 15 days (360 hours) after start of initial parenteral therapy (LMWH or UFH) (see Sections [3.1](#) and [4.1.4](#)).

Trial medication will be dispensed and should be initiated as outlined in Section [4.1.4](#).

In short, patients randomised to receive warfarin will start trial medication on the day of randomisation. They must continue to receive LMWH / UFH until the patient's INR  $\geq 2.0$  (one measurement). At that moment LMWH / UFH will be discontinued. If they are on oral anticoagulation (VKA) at the moment of randomisation, it needs to be confirmed that INR is  $< 3.0$  before trial medication is started. If the INR is  $\geq 3.0$ , warfarin must not be started until the INR is  $< 3.0$ .

Patients randomised to receive dabigatran etexilate will also start trial medication on the day of randomisation if they are not on oral anticoagulation (VKA) or if the INR is  $< 2.0$ . The first dose (capsule) of dabigatran etexilate should be given 0-2 hours prior to the time that the next dose of the initial parenteral therapy would be due, or at the time of discontinuation in case of continuous treatment (e.g. i.v. UFH).

If the patient is on oral anticoagulation with a VKA for their CVT and the INR is  $\geq 2.0$ , trial medication can be dispensed but the patient will be instructed not to start it until notified. No further parenteral anticoagulation or VKA should be given. Follow-up INRs will be performed in 1-3 day intervals until it falls below 2.0, at which time the patient will be instructed by telephone to start taking the trial medication.

Patients will take trial medication until 24 weeks after randomisation.

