	A2.15	Pre-menopausal women (last menstruation ≤ 1 year prior to Visit 1) who are pregnant, nursing, or who plan to become pregnant while in the trial.	Exclusion criterion 15 met as specified in the protocol	None
	A2.16	Patients who have participated in another trial with an investigational drug or device within the past 14 days preceding Visit 1 or who currently are participating in another trial. Patients who are still experiencing a clinical effect from an investigational drug or device.	Exclusion criterion 16 met as specified in the protocol	None
	A2.17	Patients considered unreliable by the Investigator concerning the requirements for follow-up during the trial or at the end of the trial.	Exclusion criterion 17 met as specified in the protocol	None
	A2.18	Any condition the Investigator believes would not allow safe participation in the trial.	Exclusion criterion 18 met as specified in the protocol	None
	A2.19	Active liver disease	Exclusion criterion 19 met as specified in the protocol	None

 TSAP for BI Trial No: 1160.248
 Page 16 of 30

 Proprietary confidential information © 2018 Boehringer Ingelheim International GmbH or one or more of its affiliated companies

Table 6.2: 1 Important protocol violations (continued)

Category /		Description	Requirements	Excluded
Code				from
	A2.20	Previous randomisation in this trial	us randomisation in this trial Exclusion criterion 20 met as specified	
-			in the protocol	
B	D1	Informed consent		. 11
	BI	Informed consent not available/not done	Inclusion criterion 1 not met as	All
	D1		specified in the protocol.	Neue
	B 2	Informed consent too fate	date	None
C		Trial medication and randomisation		
C	C1	Incorrect trial medication taken	Medication kit assigned not matching	PPS
	01	incorrect that incurcation taken	treatment patient was randomised to	115
			(cross-treatment) and/or not matching	
			IRT assignment	
	C2	Randomisation order not followed, e.g.	Cases will be identified from IRT	PPS
		forced randomization, misstratification	reports and read in via the manual PV	
			spreadsheet	
	C3	Non-Compliance	Compliance <80% or >120% over the	PPS
			course of the study for dabigatran	
			patients, or time in therapeutic target	
			range for warfarin patients <45%. See	
			Section 7.3 for details on compliance	
			Non compliance caused by temporary	
			interruption of the treatment due to a	
			procedure or a drop in CrCl to less than	
			30 mL/min should not be classified as a	
			protocol violation.	

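### SAP 7.3.2 drops first-week INR values rather than first-week days, so warfarin patients who stop heparin in week 1 can lose 7 to 13 later days from TTR, with error possible in either direction

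*SAP*

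**What the plan says.** SAP 7.3.2 uses the Rosendaal method and describes it this way: "assume the INR value between two measurements will vary linearly from the value of the first to the value of the second measurement". A day therefore receives a value only if it lies between two retained measurements. The same section adds: "If INR is evaluated during the first week after randomisation, those INR values will not be used in calculating TTR". It makes no exception for using a first-week value as the start of an interval. Protocol 4.3 names the Rosendaal method without any first-week exclusion, and SAP Section 4 does not list the exclusion as a change.

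The INR schedule is in Protocol 4.1.4, under the warfarin arm. Testing is daily while heparin continues. On stopping heparin it says "Initial parenteral therapy should be discontinued as soon as INR is" at least 2.0, on a single measurement. After that, testing is required "at least once every two weeks for the first three months thereafter and monthly subsequently".

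TTR feeds the cut-point tables in SAP 7.3.2 (45, 55, 60, 65 and 75%) and code C3 in SAP Table 6.2: 1. C3 removes a patient from the per-protocol set (PPS) when time in the target "range for warfarin patients <45"%, and it is one of the automatically programmed violations.

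**The concern.** Leaving the first week out of TTR is a reasonable choice. Deleting the values goes further than that. If the last INR before a two-week gap falls in week 1, the whole gap loses its left end. Days after week 1 that were bracketed by two real measurements then enter neither numerator nor denominator. They are the first days on warfarin without heparin.

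TTR describes how well the comparator was managed, and C3 uses it to decide who stays in the PPS. An avoidable distortion there can move a patient across a table cut-point or across the 45% line, and some early stoppers would have no TTR to which C3 could be applied.

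**Working it through.** The plan states no TTR figure, so there is nothing to reproduce. The check follows the SAP's interpolation rule on the protocol's minimum schedule.

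**Inputs from the documents.** Randomisation is Day 1 and end of treatment is Day 169 (Flow Chart). INR is daily until heparin stops on day d, then every 14 days at minimum. Target range is 2.0–3.0 and the C3 cut-off is 45%.

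**Assumptions.** The documents do not give the distribution of d or any INR values. I take d = 1 to 7 for the affected case and vary the INRs.

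**Days lost.** With d ≤ 7, the first retained INR is on day d+14 (day 15 to 21). Days 8 to d+13 drop out, which is d+6 days.
- d = 1: 7 days, and 7/161 = 4.3% of days 8–168.
- d = 7: 13 days, and 13/161 = 8.1%.
- If each day is assigned instead to the interval that ends on it, one more day is lost: 8 to 14 of the 162 days 8–169 (4.9% to 8.6%).
- d ≥ 8: a daily INR exists on day 8, so at most about 1 day is lost (1/162 = 0.6%).

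**Error formula.** Let T be TTR as the SAP computes it, N the days after week 1, L the days lost, and f the share of lost days in range. Keeping the anchor gives TTR = [(N − L)T + Lf]/N. Hence

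error = T − anchored TTR = (L/N)(T − f).

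The SAP figure is too high when f < T and too low when f > T.

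**Bounds**, using the larger count L = 14:

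| Patient | T | f = 0: too high by | f = 100%: too low by |
|---|---|---|---|
| Full term, N = 162 | 45% | 3.9 | 4.8 |
| | 60% | 5.2 | 3.5 |
| | 75% | 6.5 | 2.2 |
| Last INR day 56, N = 49 | 45% | 12.9 | 15.7 |
| | 60% | 17.1 | 11.4 |
| | 75% | 21.4 | 7.1 |

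**What f could be.** Take d = 7 and the next INR on day 21, interpolating day by day over the 14 lost days:
- 2.0 then 1.7: 0/14 in range.
- 2.2 then 1.5: 2.2 − 0.05k ≥ 2.0 for k ≤ 4, so 4/14 = 29%.
- 2.0 then 3.5: in range for k ≤ 9, so 9/14 = 64%.
- 2.0 then 2.5: 14/14.

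For a full-term patient with T = 60%, these give errors of +5.2, +2.7, −0.4 and −3.5 points.

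**At the C3 line**, full term, L = 14:
- All lost days out of range: a reported TTR from 45% up to 45/(148/162) = 49.3% corresponds to an anchored TTR below 45%.
- All lost days in range: a reported TTR from (45 − 8.64)/0.9136 = 39.8% up to 45% corresponds to an anchored TTR of 45% or more.
- For the 49-day patient, the upper band runs to 45/(35/49) = 63.0%.

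**No TTR at all.** With d ≤ 7 on the minimum schedule, the second retained INR falls on day d+28 (day 29 to 35). A patient with no INR by then has no interval. With the anchor, one INR after week 1 is enough.

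**The case against.** The loss is conditional. It needs heparin to stop in week 1 and no INR soon after day 7. The two-week interval is a floor, investigators may test more often, and the protocol says of its dosing aid: "This nomogram requires more frequent INR monitoring after out-of-range INR values have occurred". All of this stands, and the documents do not say how many patients meet the conditions. Two things limit the reassurance. Patients may already be on a vitamin K antagonist at randomisation, so an INR of 2.0 in week 1 is plausible. And the value that ends heparin is at least 2.0, so unless it exceeds 3.0 it is in range and does not trigger denser testing at the start of the gap.

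A reader might infer that the rule systematically flatters warfarin. The documents do not support that. Every lost interval starts at 2.0 or above. If the starting value is not above 3.0 and the next is 2.0–3.0, all lost days are in range and the SAP figure is too low. Nothing in either document gives an early in-range share. Even an assumed early share of 30–50% gives, for a completer at 45%, (13/161)(45 − 30) = +1.2 to (13/161)(45 − 50) = −0.4 points.

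A reader might also build a striking case: INR 2.1 on day 6, 1.5 on day 20, 2.6 on day 34, 2.5 on day 48. That gives 21/28 = 75% as written against 22/40 = 55% anchored. The arithmetic is right, but the 14-day wait after 1.5 conflicts with the monitoring quoted above, and the series ends at day 48 of a 24-week treatment period.

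Finally, the consequence is modest. The PPS analysis is secondary and may be skipped if fewer than 10% of the treated set are excluded. As worded, the exclusion covers only TTR, so counts of INRs in, above and below range and the monthly means still show the first week. These points stand.

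**Conclusion.** The defect is real but narrow. The SAP sentence deletes measurements where leaving the days uncounted would do. For patients who stop heparin by day 7 and are next tested at the two-week minimum, 7 to 13 bracketed days are lost. At full term and TTR of 45–75%, the error is at most roughly 4–6.5 points upward or 2–5 points downward. It is larger in early stoppers, and some of them may have no TTR, so C3 cannot be applied.

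These bounds assume the minimum schedule and all lost days on one side of the range; actual errors should usually be smaller. The number of patients affected and the net direction cannot be determined from the documents. The TTR tables and the C3 exclusion are affected. The primary analysis on the full analysis set is not, and no hypothesis is tested.

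**What to change.** Replace the SAP 7.3.2 sentence with: *Days in the first week after randomisation are not counted in the numerator or denominator of TTR; the last INR value in that week is kept as the starting point for interpolation from day 8 onward.* Keep randomisation as the time origin, as the SAP now has it; the problem does not require changing it.

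Report the number of days contributing to TTR for each patient, so that values resting on short follow-up, and patients with no TTR, are visible.

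The cost is one SAP sentence and minor programming. No new data are needed, since Protocol 4.1.4 already asks for all available INR values in the case report form. Reported TTR may shift slightly in either direction.

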7.4 PRIMARY ENDPOINT(S)

This is a prospective, randomised, open label, blinded endpoint (PROBE), active comparator trial and the clinical endpoints are being adjudicated by an AC in a blinded fashion. All analyses are exploratory, no statistical hypothesis will be tested.

The number and frequency of patients by treatment as well as by subgroup will be displayed along with the 95% confidence intervals (CIs). No difference between the treatments dabigatran etexilate versus warfarin will be tested.

Hazard ratios (HR) and 95% CI will be calculated as well; however the result will only be considered interpretable if the CI is not too wide, i.e. (lower limit of CI) \geq (estimate of HR / 4) and (upper limit of CI) \leq (4 * estimate of HR). A Cox proportional hazard model stratified by ICH at baseline will be applied.

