## **2. RATIONALE, OBJECTIVES, AND BENEFIT - RISK ASSESSMENT**

### **2.1 RATIONALE FOR PERFORMING THE TRIAL**

As in other conditions where anticoagulation is required, warfarin has many challenges and risks associated with its use. These include among others numerous drug-drug interactions, drug-food interactions, risk of bleeding and the need of regular INR monitoring.

Thus, an alternative method of anticoagulation which can be taken orally, has fewer interactions and no regular monitoring requirement would be beneficial for the post-acute care of CVT patients. Dabigatran etexilate has a marketing authorisation for treatment of DVT and PE in many countries. The aetiology of CVT can be considered sufficiently similar to other VTE [[P10-00396](#), [R15-5862](#)] to consider treatment with the same dose of dabigatran etexilate as an alternative to standard treatment with VKA. Therefore, the selected dose of 150 mg b.i.d. is expected to be as efficacious as warfarin without the burden/disadvantages associated with that drug. It can be expected that the overall bleeding risk under dabigatran etexilate will be similar to that of warfarin or potentially better.

There is currently limited but promising clinical data on the use of dabigatran in this indication. Since the incidence of CVT is very low and the occurrence of clinical endpoints is infrequent, a large confirmatory phase III trial including clinical endpoints in this indication is not feasible. Although considered a phase III trial, this trial is not designed to show statistically significant differences in clinical endpoints and is not conducted for registration purposes. The trial is designed as an exploratory trial that could provide numerical reassurance regarding net clinical benefit of dabigatran etexilate compared to warfarin. A largely comparable percentage of clinical endpoints (VTE + MBEs according to International Society on Thrombosis and Haemostasis (ISTH) definition) for both treatment arms would provide clinicians with important new information.

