### **2.2 TRIAL OBJECTIVES**

This is an exploratory trial to investigate the efficacy and safety of dabigatran etexilate versus dose-adjusted warfarin in patients with CVT after initial acute treatment.

The primary objective is to compare the net clinical benefit of the treatment arms, as measured by the composite of VTE (recurring CVT; DVT of any limb, PE, or splanchnic vein thrombosis) + major bleeding according to ISTH criteria after up to 24 weeks.

Secondary objectives include a comparison of additional efficacy and safety parameters.

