### 7.3.1 Primary endpoint analyses

The primary analysis will be based on the FAS and will use the full observation period for each patient. Patients will be analysed according to the treatment as randomised to follow the ITT principle.

The primary endpoint is defined as the number of patients with composite of VTE or major bleeding according to ISTH criteria after up to 24 weeks.

The number and frequency of patients by treatment as well as by subgroup will be displayed along with the 95% confidence intervals. No difference between the treatments dabigatran etexilate versus warfarin will be tested. Hazard ratios (HR) and 95% CI will be displayed, only if data is sufficient to do so.

The primary endpoint will also be analysed by subgroup, i.e. by stratification factor (see Section [7.6](#)). The following subgroups are of interest:

- Patients with or without ICH at baseline as assessed by the investigator. It is estimated that 30-40% of patients would present with intracerebral haemorrhage (which is a subtype of ICH) at baseline.

Further specification of analyses and further subgroups may be defined in the TSAP.

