## **7.7 DETERMINATION OF SAMPLE SIZE**

It is planned to randomise 60 patients per arm, resulting in 120 patients randomised in total. Assuming a drop-out rate of 10%, this should result in 108 evaluable patients (54 per treatment arm).

Due to the rare nature of the disease (CVT incidence of around 2 per 100.000 per year), and with limited availability of patients in this indication, the planned sample size in this trial is not based on any statistical considerations. No hypotheses will be tested or confirmed.

Data about recurrence rates for CVT patients are limited; Martinelli et al. [[R15-5570](#)] report a 5% recurrence rate after discontinuation of anticoagulation within the first year. We assume a 2-3% event rate for the composite primary endpoint with 6 months of treatment.

The trial is designed as exploratory; a comparable frequency for the primary endpoint between dabigatran and warfarin would provide clinicians with important new information.

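### The only between-arm estimate planned for the primary endpoint needs at least 8 events to pass the SAP's own width rule; the plan's assumptions give 2.4–3.6, and no risk difference is pre-specified

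*SAP*

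**What the plan says.** Protocol 2.2 states: "The primary objective is to compare the net clinical benefit of the treatment arms". Protocol 2.1 explains that the trial "could provide numerical reassurance regarding net clinical benefit of dabigatran etexilate compared to warfarin".

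For the primary endpoint, Protocol 7.3.1 and SAP 7.4 plan the number and percentage of patients per arm with 95% CIs and rule out testing a treatment difference. On a between-arm estimate, Protocol 7.3.1 says: "Hazard ratios (HR) and 95% CI will be displayed, only if data is sufficient to do so". SAP 7.4 gives this a numerical form. It says "Hazard ratios (HR) and 95% CI will be calculated as well", and on the model: "A Cox proportional hazard model stratified by ICH at baseline will be applied". It then adds that "the result will only be considered interpretable if the CI is not too wide", defined as a lower limit no less than a quarter of the estimate and an upper limit no more than four times it.

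On event numbers, Protocol 7.7 says: "We assume a 2-3% event rate for the composite primary endpoint with 6 months of treatment". It randomises 60 patients per arm and states that the sample size has no statistical basis.

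In the text provided, neither document specifies a risk difference, risk ratio or any other between-arm measure with a CI for this endpoint.

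**The concern.** The width rule is a sensible guard against over-reading an HR based on a handful of events. The difficulty is that it is set against an event count the trial is very unlikely to reach, and nothing is planned for when it fails. The pre-specified output would then be two separate proportions with two separate CIs. These do not give the difference between the arms with its uncertainty, which is what the primary objective asks about.

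A report could call the two frequencies comparable without stating how large a difference the data still allow. Readers would have to work that out themselves. Any difference and CI added to the report would be chosen after the results were known.

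**Working it through.** **Inputs**
- 60 per arm, 120 in total, 10% drop-out (Protocol 7.7). The plan's own figure reproduces: 120 × 0.90 = 108 evaluable, 54 per arm.
- Event rate 2–3% for the composite (Protocol 7.7).
- Primary analysis on all randomised patients (Protocol 7.3 and 7.3.1). Patients who discontinue early with no follow-up and no event count as having no event (SAP 6.6). The main calculation therefore uses 60 per arm.
- Width rule: both 95% limits within a factor of 4 of the HR (SAP 7.4).
- Assumptions: a Wald CI, because the SAP names no method, and the same event rate in both arms.

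**Expected events.** 120 × 0.02 = 2.4 and 120 × 0.03 = 3.6. With 108 evaluable patients: 2.2 to 3.2. The plan itself prints no event count.

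**Events needed.** The rule requires 1.96 × SE(log HR) ≤ ln 4, so SE ≤ 0.7073 and SE² ≤ 0.5003. With d1 and d2 events in the arms, SE² ≈ 1/d1 + 1/d2.
- 4 + 4: 1/4 + 1/4 = 0.50, passes (factor 3.998).
- 3 + 6: 1/3 + 1/6 = 0.50, passes.
- 3 + 5: 1/3 + 1/5 = 0.533, fails (factor 4.18).
- 2 + b: 1/2 + 1/b exceeds 0.5003 for every b up to 60, so always fails.

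A bound that does not use this approximation agrees. Each event adds at most 1/4 to the Cox information, stratified or not, so SE² ≥ 4/d and d ≥ 4/0.5003 = 7.995, i.e. 8 events.

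**Probability of meeting the rule.** Exact enumeration of two binomials. The last column is 2(1−p)^60 − (1−p)^120.

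| Event rate | P(rule met), 60 per arm | P(rule met), 54 per arm | P(an arm has no events), 60 per arm |
|---|---|---|---|
| 2% | 0.13% | 0.06% | 51% |
| 2.5% | 0.50% | 0.26% | 39% |
| 3% | 1.42% | 0.77% | 30% |

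With 60 per arm, P(rule met) reaches 50% only at a rate of 7.2%. A simulation of 20,000 stratified Cox fits (assumed 35% with ICH, no drop-out) gave 0.12%, 0.42% and 1.32%. A separate, smaller simulation (1,500 fits per rate, with 10% early censoring) gave 0.3% at 2% and 0.5% at 3%, and no fit with fewer than 8 events passed.

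**HR precision at the expected counts.** The factor is exp(1.96 × √(1/d1 + 1/d2)): 16.0 for 1 v 1, 11.0 for 1 v 2 and 7.1 for 2 v 2, against the permitted 4.

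**Risk difference at similar counts.** Newcombe 95% CI, 60 per arm, percentage points:

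| Events | 95% CI |
|---|---|
| 0 v 0 | −6.0 to +6.0 |
| 1 v 1 | −7.3 to +7.3 |
| 2 v 2 | −8.4 to +8.4 |
| 0 v 2 | −11.4 to +3.2 |

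Miettinen–Nurminen limits agree within 0.4 points for these counts. Every interval is finite, including those with no events in one or both arms.

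**The case against.** The strongest reply is that the planned display already fits the plan's declared purpose. The trial is exploratory, has no margin or required precision, and looks for broadly similar percentages in the two arms; side-by-side percentages with CIs show that. Protocol 7.4 says few outcome events are expected, and Protocol 7.3.1 makes the HR conditional on the data. The HR is still calculated when both arms have events; the rule only governs how it is read. The point difference can be taken from the planned counts, and the standard interval methods nearly agree, so choosing one late changes little.

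Much of this stands. Nothing inferential fails, the low information is not hidden, and the harm from a late choice of interval method is small. It does not close the gap. Two separate intervals do not give the uncertainty of the difference. Ruling out a test does not rule out an estimate, and Protocol 7.1 expressly allows exploratory CIs. In 30–51% of trials at the assumed rates there is no finite HR to fall back on.

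Two further points are fair. The 8-event figure assumes a Wald CI; a profile-likelihood interval at 4 + 4 has a factor of about 4.23 and would fail, so 8 is a best case. Also, SAP sections 5.3, 6.4 and 7.6 are absent from the public text, though SAP 7.4 and Protocol 7.3.1, which govern this endpoint, read as complete.

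**Conclusion.** The concern holds. Under the plan's own assumptions, the one pre-specified between-arm estimate for the primary endpoint has a 98.6–99.9% chance of failing the SAP's width rule, and no other between-arm measure is specified. The rule needs at least 8 events where 2.4–3.6 are expected.

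These figures rest on the assumed 2–3% rate, equal rates in the arms, 60 patients per arm and a Wald CI. The conclusion is not sensitive to modest error in the rate, since even odds of passing need 7.2%, more than twice the upper assumption. It should be fixed as a matter of reporting; the validity of the trial is not in question.

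**What to change.** In SAP 7.4, pre-specify as the main between-arm summary the risk difference at 24 weeks (dabigatran minus warfarin) in the FAS, from the same counts as the planned frequency table. Name one 95% CI method that remains valid with zero events: Newcombe, Miettinen–Nurminen or exact unconditional. Keep the HR and its width rule as supportive, and report the CI for the difference beside any statement that the frequencies are comparable. The full observation period can run past week 24, so the same sentence should confirm that the table and the difference both count events up to 24 weeks.

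In Protocol 7.7, note an expected CI half-width of about 7–8 percentage points. This is an average: the interval is narrower with no events and asymmetric when the arms differ.

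The cost is one sentence in each document and one table row, with no test, margin or extra patients. The drawback is that the report will show visibly wide uncertainty. The change makes the low information explicit; it does not increase it.

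### SAP 7.4 calls the primary hazard ratio interpretable only if a width rule is met, and that rule fails whenever either arm has 2 or fewer events, so the primary comparison will usually lack a usable contrast

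*SAP*

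**What the plan says.** SAP 7.4 first has counts and percentages of patients with the primary endpoint shown by arm and by subgroup, each with a 95% CI. It adds that "No difference between the treatments dabigatran etexilate versus warfarin will be tested". It then says "Hazard ratios (HR) and 95% CI will be calculated as well" and attaches a condition: "the result will only be considered interpretable if the CI is not too wide". The condition is numerical. The lower limit must be at least a quarter of the estimate, and the upper limit at most four times it. On the model: "A Cox proportional hazard model stratified by ICH at baseline will be applied".

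Protocol 7.3.1 is looser and gives no number: "Hazard ratios (HR) and 95% CI will be displayed, only if data is sufficient to do so". Protocol 7.7 plans 60 patients per arm and states: "We assume a 2-3% event rate for the composite primary endpoint with 6 months of treatment". It adds that a comparable frequency in the two arms would be informative, and does not define comparable.

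Neither document plans a risk difference or a ratio of proportions for the primary endpoint.

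**The concern.** A width limit looks like a neutral check on how much information the trial holds. With few events it is not, because the arm with fewer events controls the width of a hazard ratio interval. The same total can pass or fail depending on how it divides between the arms, and that division is the result.

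Protocol 2.2 sets the primary objective as a comparison of net clinical benefit between the arms. If the one planned estimate of that comparison carries a label telling readers to set it aside, they are left to compare two separate percentages by eye. That could happen even when the arms differ greatly.

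**Working it through.** **Inputs.** 60 randomised per arm, 1:1; 10% drop-out; 2-3% event rate (Protocol 7.7). Limits of HR/4 and 4 × HR at 95% confidence (SAP 7.4). The main calculation uses 60 per arm, because Protocol 7.3.1 bases the primary analysis on the full analysis set.

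**The plan's own figure.** 120 × (1 − 0.10) = 108, or 54 per arm. It reproduces. No power or target number of events is stated.

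**The rule in terms of events.**
- A Wald interval is HR × exp(±1.96 × SE), so both limits reduce to 1.96 × SE ≤ ln 4.
- SE ≤ 1.3863/1.96 = 0.7073, so SE² ≤ 0.500.
- With rare events and equal arms, SE² is about 1/d1 + 1/d2. Fitted Cox models with 60 per arm, unstratified and stratified, agree with this.

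**Which splits pass.**

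| Events | 1/d1 + 1/d2 | HR (approx. 95% CI) | Rule |
|---|---|---|---|
| 2 v 2 | 1.000 | 1.0 (0.14 to 7.1) | fails |
| 4 v 4 | 0.500 | 1.0 (0.25 to 4.0) | passes, just |
| 3 v 12 | 0.417 | 4.0 (1.1 to 14.2) | passes |
| 2 v 10 | 0.600 | 5.0 (1.1 to 22.8) | fails |
| 2 v 20 | 0.550 | 10 (2.3 to 42.8) | fails |
| 0 v 6 | not defined | not estimable | fails |

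With 2 events in one arm the sum always exceeds 0.500: even 2 v 60 gives 1/2 + 1/60 = 0.517. An arm with 3 events needs at least 6 in the other. No split of 7 or fewer events in total passes. The 4 v 4 split sits on the edge (SE 0.7071 against 0.7073) and passed in about 89% of stratified fits.

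**How often warfarin has 2 or fewer events** (binomial, 60 patients, protocol rate applied to warfarin).
- 2%: 0.298 + 0.364 + 0.219 = 0.881
- 2.5%: 0.219 + 0.337 + 0.255 = 0.810 (rounded)
- 3%: 0.161 + 0.298 + 0.272 = 0.731

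The chance of passing therefore cannot exceed 1 − 0.881 = 12%, 1 − 0.810 = 19% and 1 − 0.731 = 27% respectively, whatever happens on dabigatran.

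**Chance of passing with warfarin at 2.5%** (exact sum over both binomials).

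| Dabigatran rate | 2.5% | 5% | 10% | 15% | 20% | 30% |
|---|---|---|---|---|---|---|
| P(pass) | 0.5% | 3% | 13% | 18% | 19% | 19% |

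If both arms run at 2% or both at 3%, P(pass) is 0.13% or 1.4%. With 54 per arm these fall to 0.06% and 0.8%.

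**A contrast that exists for every split.** Risk difference with Newcombe 95% CI, 60 per arm: 2 v 2 gives 0.0 points (−8.4 to 8.4); 2 v 10 gives 13.3 (2.4 to 25.0); 0 v 6 gives 10.0 (2.0 to 20.1).

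**The case against.** The strongest defence is that the rule measures precision, is fixed in advance, and improves on the protocol's undefined sufficiency condition. The ratios it excludes are imprecise: 1 v 8 gives 8.0 with an interval of about 1.0 to 64. Nothing is concealed either. The SAP still calculates the HR, and the counts with per-arm intervals are not subject to the rule, so a 2 v 10 split would be plain in the primary table. Bleeding and thrombotic events also have their own endpoints, and the DMC reviews unblinded data. All of this stands. What remains is that the rule withholds interpretation from the only planned contrast, when the interval itself already shows the imprecision.

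A reader might go further and infer that the rule filters out harm and favours a finding of comparability. The documents do not support that:
- **Direction.** The rule is blind to it, so a strong benefit fails as readily as a strong harm.
- **Lopsided splits.** They do not all fail; 3 v 12 passes.
- **Parity at planned rates.** Equal splits of 1 v 1, 2 v 2 and 3 v 3 all fail, and P(pass) rises as dabigatran worsens.
- **Equal expected totals.** Parity passes more often only when event rates are well above plan (75% at 9% v 9%, against 25% at 15% on dabigatran and 3% on warfarin). Neither document assumes 9% on warfarin.
- **Reading of a pass.** Protocol 2.1 and 7.7 speak of comparable percentages or frequencies, which the rule does not touch. A pass at 4 v 4 spans about 0.25 to 4.0 and would not show comparability.

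The HR is the only between-arm estimate for the primary endpoint, not for the whole trial: Protocol 7.3.2 plans a between-arm test on the ordinal haemorrhage endpoint.

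**Conclusion.** The concern holds as a defect of usefulness, not of bias. At the planned rates the rule leaves the primary comparison without a usable contrast in about 99% or more of trials when the arms are equal. With warfarin at 2.5% it still does so in about 81% when the true excess on dabigatran is very large. Over warfarin rates of 2% to 3%, that last figure cannot fall below 88% to 73%.

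This rests on a Wald interval, similar follow-up in both arms, and 60 patients per arm. Stratification by ICH changes the outcome only for splits on the edge of the rule. A different interval type would move the boundary cases, but the arm with fewer events would still govern the width.

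The change is worth making because it costs little and gives the primary endpoint a contrast that can always be read.

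**What to change.** In SAP 7.4:
- Delete the condition that makes the HR interpretable only within the width limits.
- Always report the ICH-stratified HR with its 95% CI. Name the interval type, and use profile-likelihood or Firth-penalised limits when an arm is sparse.
- Add the between-arm risk difference with a Newcombe 95% CI, using the same denominators and the same no-event convention (SAP 6.6) as the planned percentages.
- Let the interval width convey the imprecision.

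Align Protocol 7.3.1, which makes display conditional on sufficient data, or record the departure in SAP section 4, which does not mention it.

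The cost is a few lines of SAP text, one option in the Cox procedure and one extra row in the primary table. No new data are needed. The downside is that some reported intervals will be very wide, and with no events in either arm there is still no HR, only the risk difference.
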